## 8.2 Specific Clinical Management Scenarios

### 8.2.1 Missed TB doses

Extend treatment to allow patient time to complete requisite doses.

### 8.2.2 Positive smear at M4, M6

Investigate for treatment failure, and change therapy if accompanied by clinical or radiologic deterioration or relapse of symptoms and follow local TB management guidelines.

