## **Outcome status**

### *Definition of treatment failure:*

Patient whose baseline smear (or culture) was positive and remains or becomes positive again at 5 months or later during treatment. This definition excludes those patients who are diagnosed with RR-TB or MDR-TB during treatment.

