### *Definition of treatment cure*

Patient whose baseline smear (or culture) was positive at the beginning of the treatment and is smear/ culture negative in the last month of treatment and on at least one previous occasion at least 30 days prior.

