## 6.3. Primary objective

*To determine if a Moxifloxacin-containing regimen, [Isoniazid (H), Rifampicin (R), Pyrazinamide (Z), Moxifloxacin (M)] of 24 weeks duration is superior to a control regimen [Isoniazid (H), Rifampicin(R), Pyrazinamide (Z), Ethambutol (E)] of 24 weeks duration in improving treatment outcomes in patients with recurrent TB.*

To answer the primary objective of this study the culture conversion rates will be compared between the two treatment arms at the end of the intensive phase and at month 6, where culture conversion is defined as the first of two negative (or no growth) cultures at two different visits without an intervening positive culture. This will be done by calculating the proportion of culture conversions in each of the two arms and at each of the two time points and comparing these using the chi-square test or Fisher's exact test. Log binomial regression

or Poisson regression with robust variance will also be used to improve precision of the treatment effect estimates.

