#### **6.7. Secondary objective 4**

*To compare the rates of treatment failure and recurrence of the intervention and control arm.*

This will be done by calculating the proportion of participants who do not have a negative culture result at end of treatment or who relapse post treatment in each of the two arms. The proportions will be compared these using the chi-square test or the Fisher's exact test.

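### No outcome rule says how a change of regimen for non-response is scored, and SAP 6.7 counts as non-failures some patients whom the protocol defines as failures

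*Protocol*

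**What the plan says.** Protocol 8.2.2 covers a positive smear at month 4 or month 6. The clinician is to "Investigate for treatment failure, and change therapy if accompanied by clinical or radiologic deterioration or relapse of symptoms", following local guidelines.

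Four rules then decide how such a patient is counted:

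- **Failure (Protocol, Outcome status):** a patient positive at baseline who "remains or becomes positive again at 5 months or later during treatment". RR-TB and MDR-TB are carved out: "This definition excludes those patients who are diagnosed with RR-TB or MDR-TB during treatment".
- **Cure (Protocol, Outcome status):** "smear/ culture negative in the last month of treatment and on at least one previous occasion at least 30 days prior". SAP 6.8 compares cure proportions without a definition of its own.
- **Conversion (SAP 6.3, primary):** "culture conversion is defined as the first of two negative (or no growth) cultures at two different visits without an intervening positive culture", compared "at the end of the intensive phase and at month 6".
- **Failure and recurrence (SAP 6.7):** "participants who do not have a negative culture result at end of treatment", or who relapse afterwards.

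None of the four refers to a change of the assigned regimen. SAP section 4 sets intention-to-treat for all primary and most secondary analyses. Its per-protocol set drops only data that follow a treatment interruption of three or more consecutive months caused by missed visits or an adverse event.

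**The concern.** The objective is superiority of a named regimen. When a patient deteriorates on that regimen with a positive smear and is moved to other therapy, the assigned regimen has not done its work, whatever later cultures show. If the later negatives alone decide the outcome, the assigned arm is credited with the effect of another treatment. Should such rescues be more common in the weaker arm, the month-6, cure and failure contrasts would shrink towards no difference.

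There is also a plain inconsistency about who has failed. The protocol looks at any positivity from month 5 onwards during treatment, while SAP 6.7 looks only at the result at the end. The same patient can be a failure in one document and not in the other.

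**Working it through.** **1. Rules applied to patient A:** smear-positive and deteriorating at month 4, therapy changed, culture-negative at months 5 and 6 (both are scheduled culture visits) and at end of treatment.

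| Rule | Result for A |
|---|---|
| Month-6 conversion, SAP 6.3 | Converter: two negatives at two visits, no positive between them |
| Failure, Protocol | Not a failure: nothing positive at month 5 or later |
| Failure or recurrence, SAP 6.7 | Not counted, unless relapse follows |
| Cure, Protocol (used in SAP 6.8) | Cured, if one negative falls in the last month of treatment and another at least 30 days before it |
| Per-protocol set, SAP 4 | Retained: a change of regimen is not an interruption |

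The cure result is conditional. Visits have a window of 7 days either side, so months 5 and 6 can be fewer than 30 days apart. After a change, month 6 may not be the last month of treatment.

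**2. Rules applied to patient B:** positive at month 5, therapy changed, negative at end of treatment, no relapse. The protocol scores a failure; SAP 6.7 does not. The two definitions disagree.

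**3. What is not affected.** The end-of-intensive-phase comparison is normally settled before month 4, unless that phase was extended. If the change follows an RR-TB or MDR-TB diagnosis, the protocol's failure definition excludes the patient altogether. If cultures stop after the change, SAP 5 treats the gap as missing at random, not as failure.

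**4. The plan's own figure.** Inputs from Protocol 9.1: 75% v 60%, two-sided 0.05, 80% power, continuity-corrected chi-square, N = 330. SAP 2 gives 1:1 allocation. With p̄ = 0.675 and d = 0.15:

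n = [1.960·√(2·0.675·0.325) + 0.842·√(0.75·0.25 + 0.60·0.40)]² / 0.15² = 151.9

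Corrected: (151.9/4)·[1 + √(1 + 4/(151.9·0.15))]² = 164.9, so 165 per arm and 330 in total. This reproduces the plan.

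**5. Illustrative effect on the month-6 comparison.** The documents give no rate of regimen change. *Assumption:* 60% and 75% are the rates when a change counts as non-conversion, and rescued patients are then added to the converters.

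Power = Φ{[d·√n′ − 1.960·√(2p̄(1−p̄))] / √(p₁(1−p₁) + p₂(1−p₂))}, where n′ = 165 − 2/d + 1/(165d²) for the corrected test.

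For 5% v 2% the scored rates are 65% v 77%, so d = 0.12 and n′ = 148.8. The argument is (1.464 − 1.258)/0.636 = 0.324, giving power 0.627.

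| Rescued, control v intervention | Scored rates | Power, corrected | Power, uncorrected |
|---|---|---|---|
| none | 60 v 75 | 80.0% | 83.2% |
| 3% v 1% | 63 v 76 | 68.8% | 72.9% |
| 5% v 2% | 65 v 77 | 62.7% | 67.2% |
| 3% v 3% | 63 v 78 | 82.1% | 85.1% |
| 5% v 5% | 65 v 80 | 83.7% | 86.6% |

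The loss comes wholly from imbalance between the arms.

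**6. The opposite risk, if a change were scored as non-conversion.** *Assumption:* true conversion is 60% in both arms, and 5% of control v 2% of intervention patients are changed on judgement alone although they would have converted. Scored rates are 55% v 58%. For the uncorrected test with 165 per arm, the argument is (0.03·√165 − 1.374)/0.701 = (0.385 − 1.374)/0.701 = −1.41. The chance of falsely declaring moxifloxacin superior is 7.9%, against a nominal 2.5%.

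**The case against.** The strongest reply is that this is a choice of estimand. SAP 4 adopts intention-to-treat, and counting culture results whatever happens to treatment is a legitimate treatment-policy reading of it. The alternative has its own bias. Conversion is a laboratory result, whereas the decision to change rests partly on judged deterioration in an open-label trial. Letting that judgement permanently override negative cultures could manufacture failures in one arm, as step 6 shows.

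This stands, and it decides the remedy for the primary endpoint. It does not remove the gap: the SAP never says that treatment policy is intended, and no planned analysis, per-protocol included, separates patient A from a patient who responded to the assigned regimen. It also leaves the conflict between SAP 6.7 and the protocol's failure definition untouched.

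The other limits stand too. The scenario is narrow: positive at month 4, deteriorating, changed, then negative at months 5 and 6, in a population screened for rifampicin resistance and with MDR-TB patients withdrawn. The power losses need unequal rescue. They also need 60% and 75% to be rates that count changes as non-conversion. Protocol 9.1 does not say this; its 60.1% is a retrospective cure-and-completion rate.

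A reader might also infer that 8.2.2 contradicts the failure definition because one names months 4 and 6 and the other starts at month 5. The documents do not support that. One is a prompt for management and the other an outcome definition, and they need not share months.

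**Conclusion.** The gap is real and cheap to close. On the written rules, a patient changed for non-response at month 4 who then turns negative is a month-6 converter, a non-failure absent relapse, and a cure if the timing conditions are met. Separately, SAP 6.7 scores some protocol-defined failures as non-failures.

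A reader might infer that the primary analysis is invalid, or that a change of regimen must be scored as non-conversion in it. The documents do not support either. Treatment policy is defensible for a culture endpoint in an open-label trial, and the end-of-intensive-phase comparison is normally unaffected. Nor can a definite loss of power be claimed. The fall from 80% to 69% or 63% rests on assumed, unequal rescue rates and on one reading of the planning rates; with equal rescue there is no fall. The size and direction of any bias cannot be derived from the documents.

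**What to change.** Settle the wording before outcomes are examined by arm.

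- **SAP 6.7 and 6.8:** count a change of the assigned regimen for inadequate bacteriological or clinical response as treatment failure and as not cured, not reversed by later negative cultures. Align 6.7 with the protocol so that positivity at 5 months or later during treatment counts as failure.
- **SAP 6.3:** state that month-6 conversion is analysed by culture result regardless of regimen change (treatment policy). Pre-specify a sensitivity analysis that scores a change for non-response as non-conversion, and report both.
- **Reporting:** give the number of regimen changes for non-response in each arm.

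The cost is a few sentences in the SAP and a flag built from existing treatment records. Cure proportions may be slightly lower and failure proportions slightly higher. The main downside is that the decision to change is an open-label clinical judgement, so composite scoring can itself be biased by knowledge of arm. That is why it is only a sensitivity analysis for the primary endpoint and why the counts by arm should be shown. No change to the clinical rule in Protocol 8.2.2 is proposed.

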### 8.2.3 MDR TB

Patients withdrawn from study because their initial TB isolate is found to be MDR –TB will not be followed up further, unless required for patient safety (e.g. an adverse event present, in which case follow-up should occur as clinically indicated).

### 8.2.4 Withdrawal of study drug

An investigator may withdraw one or all drugs in the study treatment in the event of a serious or life-threatening adverse event, if this is deemed to be in the patients' best interest. This needs to be discussed with the study PI or designee before the decision is made, unless in an emergency situation. All safety issues need to be followed up until resolution to  $\leq$  Grade 2 (DAIDS Table for Grading Adult and Paediatric Toxicity Events)

### 8.2.5 Reporting AE's

The study drugs are Moxifloxacin, Ethambutol, Isoniazid, Rifampicin, and Pyrazinamide. The most common adverse effects known to be associated with the study drugs are summarized in the protocol (see Table 4 above). The investigators are responsible for reporting all Grade 3 and Grade 4 adverse events that are observed or reported during the study, regardless of whether they are thought to be related to the study drugs in patients chart notes. All Adverse Events including SAEs will be reported in accordance with ICH and SA GCP guidelines.

## 8.3 Guiding Principles of Adverse Event Management

For adverse events, that is in the investigator's judgment may be due to study drugs, the following approach to management should be applied:

### 8.3.1 Grade 1 Adverse Events

In general, for grade 1 events the patient will be followed carefully and the study drugs will be continued.

### 8.3.2 Grade 2 Adverse Events

For grade 2 events the patient will be followed more closely, with additional laboratory and/or clinic visits as necessary; drugs should be continued unless in the view of the investigator this would be unsafe.

### 8.3.3 Grade 3 and 4 Adverse Events

Any grade 3 or 4 event should be carefully assessed. The research clinician should rule out other possible causes of the symptoms before discontinuing study medication. When possible, concomitant medications should be with-held first at the discretion of the research clinician if causality is suspected. If after careful assessment and in the clinician's judgment the event is due to study drug(s), the causative study drug(s) may be withheld. The patient should be permanently discontinued from study medications if it is in their best interests to do so. Further treatment of the TB will be directed by the clinician in consultation with the investigator. The patient will continue to be followed according to the protocol. Other adverse events of any grade not thought to be due to the study drugs, should be managed at the discretion of the research clinician; study treatment should be continued, if possible.

## 8.4 Reporting Serious Adverse Events (SAEs)

The following Serious Adverse Event will be reportable to the database and regulatory authorities: AE's that:

- Results in death
- Is immediately life threatening at the time of occurrence
- Results in persistent or significant disability or incapacity
- Requires in-patient hospitalization or prolongs hospitalization
- Results in a congenital anomaly or birth defect
- Is deemed an "important medical event" by the Investigator (may not be immediately life threatening or result in death or hospitalization but may jeopardize the patient e.g. convulsions. This will include any adverse event that *is unexpected, but related* to the study product, e.g. asymptomatic prolonged QT interval associated with Moxifloxacin.

## 8.5 Safety Monitoring

### Procedures for assessing safety

At each clinic visit patients will be asked about changes (adverse events) that have occurred since their previous visit. Physical assessments will be performed at baseline and on subsequent scheduled visits.

Safety laboratory investigations will be performed at screening and in accordance with the schedule of evaluations, as well as determined by the study clinician based on the evaluation.

1. Screening tests and scheduled subsequent visits will include: Liver function, renal function, full blood count: At screening, baseline and every second month until Month 8 of follow up. Thereafter, tests will be performed at the end of TB treatment, time of TB recurrence and at the study termination visit.
2. 2. Pregnancy test: At screening, baseline and every month thereafter as per the SoE.

For isolated asymptomatic or symptomatic Grade 3 elevation of total bilirubin all medications should be discontinued and held for up to 14 days until levels and symptoms are Grade  $\leq 2$ , at which time therapy may be reintroduced. If there is  $\geq$  Grade 2 elevation of total bilirubin with transaminase elevation of grade  $\geq 3$ , this

should be treated as Grade 4. If Grade 3 toxicity develops after re-introduction of the study medications or if the Grade 3 toxicity does not resolve within 14 days, then the participant will be discontinued from study medications. The participant will continue to be followed on study, off study drugs. All medications may be restarted if the laboratory abnormalities were thought secondary to a concomitant illness.

Participants who develop Grade 4 elevations of the total bilirubin will be discontinued from study medications. The participant will continue to be followed on study, off study drugs.

Any additional test that the investigator deems necessary for the clinical evaluation of the subject can be performed.

Any adverse events detected will be graded according to a modified version of the toxicity criteria produced by the Division of AIDS and coded using MedDRA.

### QTc Prolongation

Participants in this trial may receive Moxifloxacin which has the potential to prolong the QTc interval. All QTc measurements will be corrected with the Fridericia correction.

The protocol-specific criteria for grading prolonged QTc are as follows:

PARAMETER	GRADE 1 MILD	GRADE 2 MODERATE	GRADE 3 SEVERE	GRADE 4 POTENTIALLY LIFE- THREATENING
Prolonged QTc (using Fridericia QT correction formula)	Asymptomatic, QTc interval 0.45 – 0.47 sec	Asymptomatic, QTc interval > 0.47- < 0.50 sec	Asymptomatic, QTc interval $\geq$ 0.50 sec OR a QTc > 0.48 sec with an increase in interval $\geq$ 0.06 sec above baseline	Life threatening consequence, eg, Torsade de pointes or other associated serious ventricular dysrhythmia

If Grade 2 QTc prolongation develops during the course of the study and is felt to be due to study medications, the participant will be monitored more closely, with twice weekly visits and QTc evaluation. If Grade 3 QTc prolongation occurs, all study drugs will be discontinued and the participant will be referred to hospital for further assessment and management. If the QTc prolongation is considered most likely to be due to concomitant illness or medication, standard management, including discontinuation of the likely causative agent, should be undertaken.

If a participant develops Grade 4 QTc prolongation, he or she will be hospitalized and discontinued from study medications. If the prolongation is felt to be caused by a concomitant medication and resolves with discontinuation of that agent, study medications may be restarted. Otherwise, the participant will be referred to the NTP for treatment of his or her TB according to local standards of care. The participant will continue to be followed on study, off study drugs.

Serious adverse events will be reported to the MCC and the UKZN Biomedical Research Ethics Committee. (BREC) according to their specific requirements.

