**Table 1: Study Regimens**

Study Regimens		
	Intensive phase	Continuation phase
Intervention Arm *	HRZM daily (first 2 months )	HRM daily (4 months)
Control Arm **	HRZE daily (first 2 months )	HR daily (4 months )

H – Isoniazid; R – Rifampicin; Z – pyrazinamide; E – Ethambutol; M - Moxifloxacin

\* When patients become smear negative, they will be switched from the intensive phase to continuation phase with Isoniazid, Rifampicin and Moxifloxacin for 4 months

\*\*When patients become smear negative, they will be switched from the intensive phase to continuation phase with RIF and INH for 4 months.

In this study the total duration of TB therapy will be 24 weeks (6 months) for the Intervention Arm, and the Control Arm. The duration of TB treatment may increase due to a delay in the time to sputum conversion. This will result in the extension of TB treatment beyond 6 months.

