3: PK blood samples, in the intervention arm only, will be taken once during the intensive phase of TB treatment at either Week 4 **OR** Month 2 (**PK bloods may be repeated at Month 2 if these were not taken, incorrectly done or incomplete at Week 4 OR at the discretion of the investigator**), and at the end of TB treatment (Month 6)

4: Additional PK samples will be taken at M7 (or the first visit after if Month 7 is missed) in Intervention Arm before and after the ingestion of the single additional dose of Moxifloxacin. This additional PK sample may be deferred to month after TB treatment completion on participants who have TB treatment extended beyond 6 months

5: If PBMCs are not collected at baseline samples may be taken at Week 4 or Month 2

6. End of TB Treatment visit will be conducted within 7 days of completion of TB treatment.

\* Samples will be collected and stored for future susceptibility testing,

\*\*ECG's will be done at baseline, Month 2 and Month 4 and Month 6. ECG's will be performed 2 monthly during treatment with Moxifloxacin

\*\*\*Additional PBMC's will be collected at IRIS and at the time of seroconversion

The study SoE will be followed except when procedures are clinically indicated as not required.

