## 8.0 CLINICAL MANAGEMENT ISSUES

### 8.1 Clinical Management Issues

The IMPRESS study will use the Division of AIDS Table for Grading the Severity of Adult and Paediatric Adverse Events (DAIDS AE Grading Table) Version 1.0, December 2004 (Clarification, August 2009)

- Patients need to be assessed for evidence of musculoskeletal toxicity at every study visit through history taking and physical examination.
- Ocular toxicity will be assessed using the Snellen and Ishihara tests at baseline and month 2 and/or when clinically required (Control Arm only). Patients will be educated about symptoms of ocular toxicity before treatment initiation, and will be assessed for ocular toxicity for the duration of TB therapy when Ethambutol forms part of the TB regimen. The Snellen and Ishihara tests will be repeated if any symptoms of ocular toxicity or any change in vision occurs.

- All patients will undergo ECG monitoring at baseline, Month 2, Month 4, Month 6 (and 2 monthly whilst being administered with Moxifloxacin). This will be repeated if patients complain of chest pain or syncope. Moxifloxacin will be substituted for Ethambutol if there is evidence of QT prolongation, or if patients QRS complexes change in amplitude from baseline.
- Patients must not have evidence of severe or life-threatening liver disease at baseline (Bilirubin, AST and ALT < 5 times the ULN), no evidence of renal impairment i.e. creatinine clearance of > 60 mls/min, serum potassium of > 3.0 mmol/l.

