#### **6.5. Secondary objective 2**

*To compare the proportion of patients with any Grade 3 or 4 adverse reactions*

Adverse events occurring during the study will be summarised in frequency tables by arm. The frequencies of Grade 3 and 4 adverse events will be compared between the two arms using the Fisher's exact test.

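### ECG follow-up after a Grade 2 QTc depends on attribution to study drugs, and after Month 6 on moxifloxacin, so asymptomatic Grade 3 QTc may be found more often in the intervention arm; SAP 6.5 needs a supplementary analysis by ECG source

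*Protocol*

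**What the plan says.** **Common to both arms.** Protocol 8.1 states: "All patients will undergo ECG monitoring at baseline, Month 2, Month 4, Month 6 (and 2 monthly whilst being administered with Moxifloxacin"). The Schedule of Events (Table 5) shows the same four time points. On symptoms, 8.1 adds: "This will be repeated if patients complain of chest pain or syncope". Neither rule is limited to one arm up to Month 6.

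**Depends on attribution.** In the QTc Prolongation part of protocol 8.5, a Grade 2 QTc leads to intensified follow-up if it is "felt to be due to study medications, the participant will be monitored more closely, with twice weekly visits and QTc evaluation". No end date is given and no arm is named.

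**Depends on moxifloxacin.** A footnote to Table 5 says: "ECG's will be performed 2 monthly during treatment with Moxifloxacin". This adds ECGs only when treatment is prolonged, which the text under Table 1 allows in either arm: "The duration of TB treatment may increase due to a delay in the time to sputum conversion".

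**Context for attribution.** The trial is open label (protocol Schema and 3.0). Table 4 lists a prolonged QT interval for moxifloxacin and for no other study drug, and the QTc section opens by naming moxifloxacin. Neither document describes ECG reading or attribution blind to arm.

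**Analysis.** SAP 6.5 states: "The frequencies of Grade 3 and 4 adverse events will be compared between the two arms using the Fisher's exact test". It does not distinguish events by how they were found.

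**The concern.** The protocol defines Grade 3 QTc as an asymptomatic ECG finding: at least 0.50 s, or above 0.48 s with a rise of at least 0.06 s over baseline. Such an event is recorded only if an ECG is taken while the threshold is exceeded, so the number of patients with a Grade 3 depends directly on the number of ECGs.

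Take two patients with the same Grade 2 reading and the same later QTc course. The one on moxifloxacin is likely to have the prolongation attributed to study drug and to be seen twice a week. The one on ethambutol is less likely to be, and then has an ECG only at the next scheduled visit. In extended treatment, the moxifloxacin patient keeps having two-monthly ECGs and the control patient has no matching one.

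Secondary objective 2 is the planned between-arm safety comparison. A difference in Grade 3 QTc there could partly reflect how often the ECG was taken, in the direction unfavourable to moxifloxacin. As the SAP stands, no planned output would show how much.

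**Working it through.** **The plan's own figures.** The documents give no figure for QTc or Grade 3/4 events. The one related figure is the sample size. The continuity-corrected two-proportion formula at 75% v 60%, two-sided 0.05 and 80% power gives 165 per arm, 330 in total, as stated in protocol 9.1. The 165 is used below.

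**ECG counts from the schedule.**
- Scheduled on-treatment ECGs to Month 6: 3 in each arm (Months 2, 4, 6).
- Grade 2 found at Month 2 (week 8 of 24) and attributed to study drug: 2 per week x 16 weeks = 32 evaluations to the end of treatment.
- Same finding, not attributed: 2 (Months 4 and 6).
- Ratio 32/2 = 16, but only in patients who reach Grade 2.
- After Month 6, extended treatment: two-monthly on moxifloxacin, none scheduled in control. The number of such patients is not given, so this part is not sized.

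**Illustration 1: assumed inputs, identical true QTc behaviour in both arms.** Let G be the proportion reaching Grade 2, q the chance that one later ECG reads Grade 3, a the proportion attributed to study drug, and D(k) = 1 - (1 - q)^k the chance of at least one Grade 3 reading in k independent ECGs. Then

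P(detected Grade 3) = G x [a x D(32) + (1 - a) x D(2)]

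spurious excess = G x (a_int - a_con) x [D(32) - D(2)].

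Assumed: a_int = 90%; a_con = 0 to 50%; G = 2 to 10%; q = 1 to 5%.

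| Case | G | q | a_con | D(32) | D(2) | Excess |
|---|---|---|---|---|---|---|
| Low | 2% | 1% | 50% | 0.275 | 0.020 | 0.02 x 0.40 x 0.255 = 0.2 points |
| Mid | 5% | 3% | 25% | 0.623 | 0.059 | 0.05 x 0.65 x 0.564 = 1.8 points |
| High | 10% | 5% | 0% | 0.806 | 0.098 | 0.10 x 0.90 x 0.709 = 6.4 points |

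In the mid case the expected numbers with a detected Grade 3 are 4.7 of 165 against 1.6 of 165.

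**Illustration 2: assumed QTc distribution.** Take one 8-week gap between scheduled ECGs: 2 x 8 + 1 = 17 ECGs if attributed, 1 if not, with attribution 100% in intervention and 0% in control. Assume an underlying mean of 0.475 to 0.485 s, a visit-to-visit SD of 0.008 to 0.015 s, independent readings, and only the 0.50 s criterion. At 0.480/0.012 the chance per ECG is P(Z >= 1.67) = 4.8%, and over 17 ECGs 1 - 0.952^17 = 56.5%. With G = 10% the excess is 0.10 x (0.565 - 0.048) = 5.2 points, or about 8.5 patients of 165. Over the grid it is 0.1 to 7.9 points with G = 10%, and 0.03 to 1.6 points with G = 2%.

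**Effect on the SAP 6.5 test.** Assume a 10% background of any Grade 3/4 event and 165 per arm. The chance that Fisher's exact test gives p <= 0.05 is:

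| Spurious excess (points) | 0 | 1 | 2 | 4 | 6 | 8 |
|---|---|---|---|---|---|---|
| Chance | 3.1% | 3.9% | 6.2% | 15.6% | 31.1% | 49.9% |

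**The case against.** **The trigger is neutral as written.** It names no arm, and protocol 8.2.5 counts the control drugs as study drugs: "The study drugs are Moxifloxacin, Ethambutol, Isoniazid, Rifampicin, and Pyrazinamide". Section 6.2 also says that the Table 4 list is not exhaustive. A reader might infer that QTc is searched for far harder across the whole intervention arm. The documents do not support that: scheduled ECGs to Month 6 and symptom-triggered ECGs are equal, and the imbalance is inferred from likely attribution in an open-label setting. The inference is reasonable, but it is an inference.

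**Grade 4 is different.** It is defined by a life-threatening clinical event and depends much less on ECG frequency. The point is confined to asymptomatic Grade 3.

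**Other adverse events.** A reader might infer that the extra visits inflate non-QTc events too. Protocol 8.5 says: "At each clinic visit patients will be asked about changes (adverse events) that have occurred since their previous visit". A patient with fewer visits is therefore asked about the same interval at the next one, and the extra visits specify QTc evaluation, not laboratory tests. That extension is weak.

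**The size is assumed.** This stands. In Illustration 2 the share of Grade 3 detections that come only from the extra ECGs is 83 to 94%, but for rare readings it tends to 16/17 = 94% whatever the QTc, and it applies only to patients already at Grade 2. Regression to the mean after one high reading matters: at mean 0.465 and SD 0.012 the excess falls to about 0.3 points. Correlated readings would also lower it. The second Grade 3 criterion is left out, and investigators may order extra ECGs in either arm (8.5).

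**A restricted analysis has its own bias.** This also stands. Grade 3 stops all study drugs, so a true event found at a twice-weekly visit may have resolved by the next common ECG. That rules out making the restricted version the formal test, but not showing it beside the full one.

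**Conclusion.** The concern holds in a limited form. After a Grade 2 QTc, and during treatment extended past Month 6, ECG follow-up depends on attribution or on moxifloxacin. It is therefore likely to be denser in the intervention arm and can inflate that arm's count of asymptomatic Grade 3 QTc. SAP 6.5 has no analysis that would show this.

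The size cannot be derived from the documents. It rests on assumed Grade 2 frequency, attribution rates, QTc variability and independence of readings. On those assumptions the spurious excess is about 0 to 8 percentage points, with a mid case near 2. At 2 points the Fisher rejection rate moves from 3.1% to 6.2%, given an assumed 10% background. The effect is small if Grade 2 QTc is rare and material only if it is common.

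A reader might also conclude that the bias could never be separated from a drug effect. That goes too far: if the reason for each ECG is recorded, its contribution can be shown. Without a pre-specified rule, though, the separation would be post hoc.

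**What to change.** 1. Keep the all-event Fisher comparison in SAP 6.5 as the formal test.
2. Flag each ECG as common scheduled, symptom-triggered, attribution-triggered, or moxifloxacin-only after Month 6, and carry the flag to any QTc adverse event first found on it.
3. Add two pre-specified supplementary analyses to SAP 6.5:
   - (a) the proportion of patients with Grade 3 QTc by arm at the common on-treatment ECGs (Months 2, 4 and 6);
   - (b) the Grade 3/4 comparison with and without QTc events first found at attribution-triggered or moxifloxacin-only ECGs, with those events listed by arm.
4. State that the restricted results are read beside the all-event result and do not replace it, because they may miss true events once Grade 3 has stopped study drugs.

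The cost is one SAP paragraph, one data flag and a little more analysis work. Patient monitoring is unchanged.

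Separately, protocol 8.1 describes a drug substitution on evidence of QT prolongation, while the QTc Prolongation section describes closer monitoring at Grade 2 and stopping of all study drugs at Grade 3. These are different responses to the same finding, and they also affect how long a patient stays under moxifloxacin-linked ECGs. The sponsor must reconcile the two sections.
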